4.2 Intervention

CBT-C and ERT-C are each 8-session, individual, caregiver-directed interventions delivered by a trained study therapist listed on the face page and facilitated by a manualized workbook (Appendix A and Appendix C) with between-session practice exercises (Appendix B). To accommodate caregivers and reduce compliance issues with attendance of sessions, the 8 sessions are to be completed within 8 to 16 weeks from initiation of the first session. Each session is 60 minutes in length and will be audio and video recorded for MSK participants; sessions will only be audio recorded for MGH participants. Specific modules and intervention components are described below. To accommodate as many caregivers as possible and in response to the restrictions placed on caregivers currently in the context of the COVID-19 pandemic, sessions will be offered via telepsychiatry using a platform approved by each site's respective Privacy Board (e.g. Webex, Zoom, Teams).

Cognitive Behavioral Therapy for Cancer Caregivers (CBT-C)

Cognitive Behavioral Therapy (CBT) is an evidence-based psychotherapeutic approach that is grounded in the cognitive model that purports that a person's emotional, behavioral, and physiological reactions to a situation is based on their appraisal of that situation. The focus of therapy is on changing cognitions and beliefs about a situation and altering automatic behavioral responses evoked by that perception. CBT aims to improve emotion regulation by challenging and changing unhelpful cognitions and behaviors and improving personal coping strategies. Modules incorporate skills for relaxation and information specific to the caregiving context throughout. Caregivers in this arm will practice relaxation skills using study mediation recordings as described in the CBT-C manual (Appendix C). Meditation recordings will be sent to participants via email. The CBT-C manual used in this study was specifically developed for use with cancer caregivers in previous psychotherapy trials at Massachusetts General Hospital.

The sessions are outlined as follow:

- 1) psychoeducation, goal-setting, and describing the rationale for CBT (Session 1);
- 2) coping effectiveness training (Session 2);
- 3) identifying unhelpful cognitions and dysfunctional beliefs (Session 3);

- 4) challenging and restructuring unhelpful cognitions (Session 4);
- 5) behavioral activation within the limitations of the caregiving context (Session 5);
- 6) problem-solving (Session 6);
- 7) communication strategies and assertiveness training (Session 7);
- 8) consolidating gains, maintenance, and relapse prevention (Session 8).

Emotion Regulation Therapy for Cancer Caregivers (ERT-C) Emotion Regulation Therapy for Cancer Caregivers (ERT-C) is an 8-session intervention that builds upon the foundations of CBT and addresses earlier motivational processing components of the caregiver context while targeting earlier and later components of internal distress and resultant maladaptive behavioral coping. ERT-C utilizes modules to train caregivers in: 1) cue detection and delineation of problematic motivational (i.e., threat and/or loss-based) and regulatory (i.e., worry, rumination, self-criticism, reassurance seeking, avoidance/withdrawal, and/or compulsive behaviors) responses within evocative and burdensome caregiver contexts; 2) attentional skills to increase the ability to broaden, shift, and sustain attention when distressed; 3) meta-cognitive skills to more effectively distance and reframe emotional thoughts; and 4) improving the ability to more adaptively engage contexts that are intrinsically rewarding even when accompanied by loss/threat via contextual application of learned skills.

The sessions are outlined as follow:

- 1) psychoeducation and motivation/dysregulation cue detection within caregiving contexts (Session 1);
- 2) attention regulation skills training (Sessions 1-2);
- 3) training in metacognitive skills (Sessions 3-4);
- 4) exposure to proactive living in the face of risk and loss while applying skills (Sessions 5-7);
- 5) consolidating gains, taking larger proactive steps, and relapse prevention (Session 8).

Selection, Training and Supervision of Study Therapists. We will carefully consider selection of therapists and provide intensive training and supervision of providers. Therapists will be drawn from disciplines of psychology, psychiatry and social work with appropriate training and knowledge of individual therapeutic dynamics. Therapists will be assigned to either the ERT-C or CBT-C arms to maximize differentiation between formats. Interventionists will include both salaried research team members and pre- and post-doctoral trainees from the Department of Psychiatry and Behavioral Sciences at MSK and the Center for Psychiatric Oncology and Behavioral Sciences at MGH Cancer Center. All interventionists will undergo extensive training in ERT-C (by Drs. [name] and [name]) or CBT-C (by [name] and [name]) during an initial two-day intensive training workshop during the first year of the study. Trainings will occur over Webex or Zoom so that all study therapists at both sites will be able to attend. After the first year of the study, the investigative team will conduct annual day-long training in the delivery of these interventions. These booster

trainings will also be conducted via Webex or Zoom and will serve two purposes: (1) to address and refine the therapeutic skills of existing study therapists; and (2) to provide training to any new therapists who joining the study team after the first year of the grant. Therapists will be given the treatment manual (ERT-C Manual: Appendix A; CBT-C Manual: Appendix C) for the intervention they are providing, describing in detail the philosophy, format, and techniques involved. Manuals will focus on skills acquisition in the conduct of each intervention. All therapists will receive continual training during weekly supervision sessions to maintain standardized delivery and prevent “provider drift.” Therapists without prior ERT experience will be assigned a training case patient who will be consented onto the study. Participants who are consented as training cases will not be randomized and will not complete any assessments. Data collected on training cases will be used for training and supervision purposes on this study only. These records will not be shown outside of the study supervisors, therapist in training, and staff.

Fidelity to Intervention. We will institute best practices to enhance and monitor fidelity, including: careful attention to the study design, selection, intensive training and supervision of treatment providers, delivery of treatment, receipt of treatment, and “real-life” enactment of treatment skills. In terms of study design, we will compare two intervention conditions (ERT-C and CBT-C) equivalent in the number, frequency and duration of sessions. We will monitor session attendance using a diary log with names and session dates to track percentage of attendance and account for absenteeism and reasons for missed sessions, which will be assessed with an open-ended question for enrolled participants who withdraw. To reduce likelihood of treatment contamination, each condition will be delivered by distinct treatment providers. We have developed comprehensive treatment manuals for ERT-C and CBT-C to facilitate standardized delivery. Therapists will monitor attendance and homework completion as part of their process notes. Deviations from protocol will be recorded and discussed regularly during supervision. We will also externally monitor treatment sessions and provide feedback to interventionists. To ensure providers are adhering to the treatment protocol, the manuals include a checklist/outline of intervention components for each session. We have also developed Treatment Integrity Coding Manuals for each of the two interventions (ERT-C, CBT-C). These manuals allow independent raters to evaluate each session of both interventions for treatment adherence in terms of process and content (e.g., ERT-C-specific v. CBT-C-specific content). All sessions will be audio and video recorded (MSK participants) or audio recorded (MGH participants), with prior consent of the participants. A random sample of 30% of cases (100% of audio/video taped sessions for these participants) will be evaluated and rated for treatment integrity (utilizing the Treatment Integrity Coding Manual) by consultants Drs. [name] and [name], each of whom has considerable experience in conducting ERT-C and CBT, respectively. To prevent against therapist drift, treatment integrity ratings will be conducted regularly throughout the study. Raters will offer written feedback to individual facilitators regarding the specific individual session to enhance continued training and supervision in these individual interventions. Raters will not be blinded to the therapist, intervention arm, or the specific session within that treatment. Feedback on audio/video recorded sessions will also be incorporated into supervision sessions.

5.0 THERAPEUTIC/DIAGNOSTIC AGENTS & NON-THERAPEUTIC ASSESSMENTS

MEASURE/ASSESSMENT	Validated	Construct/Domain Assessed
Demographic Information and Psychosocial Services Use, Preferences, and Perceived Barriers	No and not validating	Background and demographic information
Distress Thermometer (DT)	Yes	Caregiver Distress
Hospital Anxiety and Depression Scale (HADS)	Yes	Anxiety and Depression
Penn State Worry Questionnaire	Yes	Worry
Rumination-Reflection Questionnaire, Rumination subscale	Yes	Rumination
Attentional Control Scale	Yes	Attentional focus and shifting ability
Experiences Questionnaire, Decentering subscale	Yes	Disidentification with negative thinking
Emotion Regulation Questionnaire, Reappraisal subscale	Yes	Emotion regulation capacity
Caregiver Quality of Life Index-Cancer	Yes	Quality of life
Caregiver Reaction Assessment (CRA)	Yes	Caregiver burden
Self-Administered Comorbidity Questionnaire (SCQ)	Yes	Comorbid medical problems
Patient-Reported Outcomes Measurement Information System Global Health Scale (PROMIS-GH)	Yes	Global mental and physical health.
Credibility and Expectancy Questionnaire	Yes	Expectation of treatment outcome
EORTC QLQ-C30	Yes	Cancer patient quality of life
Perceived Stress Scale	Yes	Perceived stress
National Survey on Drug Use and Health, Healthcare Utilization	Yes	Healthcare service utilization
Working Alliance Inventory-Short Form (WAI-SF189)	Yes	Therapeutic alliance

6.0 CRITERIA FOR PARTICIPANT ELIGIBILITY

6.1 Participant Inclusion Criteria

Caregivers

- 1) As per self-report, age 18 years or older.
- 2) As per self-report, are a current caregiver to an MSK or MGH patient with any site/stage of cancer who has received any type of treatment (e.g. curative, palliative) in the past 12 months.
- 3) Experience distress as evidenced by a score of 4 or greater on the Distress Thermometer (DT) **and** answer “Yes” to at least one of the follow-up questions (i.e.

reporting that their distress is related to their caregiving experience, **or** their distress started or is related to caregiving or has gotten worse since the patient was diagnosed or began treatment). (N/A for training case participants)

- 4) English fluent: Self-report by subject identifying English as the preferred language for healthcare, and self-reported degree of fluency as speaking English “Very well.”
- 5) As per self-report, residing in New York or New Jersey (for MSK participants), or Massachusetts (for MGH participants), or have the ability to complete sessions while complying with current telehealth regulations.

Patients

- 1) Age 18 years or older as per EMR.
- 2) Patient of an eligible caregiver, as per self-report or the EMR.
- 3) English speaking as per the EMR or self report by subject identifying English as the preferred language for healthcare, and self-reported degree of fluency as speaking English “Very well.”.

6.2 Participant Exclusion Criteria

Caregivers

- 1) As per self-report, presence of disorder that compromises comprehension of assessments or informed consent information (e.g., dementia).
- 2) As per the judgement of the consenting professional, clinical, PI, and/or as per the medical record, severe psychopathology or cognitive impairment which is likely to interfere with the participation or completion of the protocol or their ability to provide meaningful information.
- 3) As per self-report, currently engaged in regular individual psychotherapeutic support (that the participant is unable or unwilling to put on hold for the course of treatment).
- 4) As per self-report, a lifetime history of bipolar disorder, schizophrenia, or schizoaffective disorder.
- 5) As per self-report, has medical condition or medication use known to confound measures of systemic inflammation (e.g., autoimmune disorder, inflammatory disease; uncontrolled thyroid disease; active infection; myocardial infarction or stroke in the last 6 months; Type I diabetes; acute hepatitis; vaccination in the last 7 days for viral disease). (N/A for training case participants)
- 6) As per self-report, is a regular smoker, defined as having more than 2 cigarettes per day on most days. (N/A for training case participants)
- 7) As per self-report, providing care for a patient who has a caregiver currently or formerly enrolled in this study (‘formerly enrolled’ is N/A for training case participants).
- 8) As per self-report, currently enrolled in another study focused on supportive care for caregivers (MGH participants only).

Patients

- 1) Presence of disorder that compromises comprehension of assessments or informed consent information (e.g., dementia) as per EMR or clinician judgment.
- 2) As per the judgement of the consenting professional, clinical, PI, and/or as per the medical record, severe psychopathology or cognitive impairment which is likely to interfere with the participation or completion of the protocol or their ability to provide meaningful information

7.0 RECRUITMENT PLAN

A total of 480 participants (240 caregiver participants and 240 patient participants) will be enrolled at MSK and MGH. MSK will recruit 130 caregiver participants and 130 patient participants; MGH will recruit 110 caregiver participants and 110 patient participants. Participants will be recruited from outpatient clinics in various departments at Memorial Sloan Kettering Cancer Center (MSK) and MGH, including the Psychiatry, Social Work, Thoracic, Gastrointestinal, Breast and Bone Marrow Transplant services. Participants will not be recruited from the Neurology Services at MSK and MGH as both sites have several competing protocols for caregivers. Participants will also be recruited from the MSK Ralph Lauren Center (RLC). Caregiver enrollment is not contingent on patient enrollment, and contact with patients is not needed in order for caregivers to be contacted, consented and enrolled.

As referenced in section 4.1, training case participants will be identified and consented onto the study for training purposes only. Training case participants will not be required to screen in with study measures (i.e. distress screening).

There will be three strategies to recruit caregiver and patient participants at MSK and MGH:

1) *Flyers and advertisements*: Flyers will be posted (either digitally or paper with the clinic's permission) in the above-named clinics with contact information for the study team (Appendix D and Appendix E). Flyers will also be posted on the MSK Caregiver website (www.mskcc.org/caregivers) and on MGH Cancer Center website pages on Supportive Care and Caregiving (www.massgeneral.org/cancer-center/patient-and-family-resources/supportive-care).

Individuals interested in learning more regarding the study will contact the research study team. If contacted over the phone, a trained consenting professional will explain the study details, verify eligibility and screen the prospective participant with the Distress Thermometer. If eligible, the individual will be consented using the verbal consent script. The study information sheet will be emailed or mailed to the caregiver. At MGH, individuals may also be consented by electronic informed consent (EIC).

2) *Remote recruitment*: The research team will provide study invitation packets for caregivers identified by the clinicians or by the study team with clinician approval in MSK and MGH clinics. Clinicians will provide the study team with the names of caregivers with the caregivers verbal permission, and the study team will be responsible for providing caregivers with the packet. This invitation packet will include an introductory letter describing the study (Appendix F), a study flyer (Appendix D), and a contact number for the PI and study team. Within approximately two weeks of mailing the invitation packet, the consenting professional will call/email potential participants to introduce the study (Appendix R). The study team will make between 3 and 5 follow-up calls/emails, varying the time of the call (morning, afternoon, evening and day of the week) and leaving no more than 3 messages and/or emails. All emails sent to prospective participants will be sent securely using secure email (i.e. MSKSecure and MGH Send Secure).

We will also utilize the MSK Facebook page in collaboration with the MSK Communications Office to circulate an advertisement for this study (Appendix U).

Caregivers will also recruited from the Counseling Center in the Department of Psychiatry and Behavioral Sciences. When caregivers who are seeking care in the Caregivers Clinic speak with the Triage Coordinator, they will first be offered a session with one of the treating psychiatrists, psychologists or APPs staffing the Clinic. They will also be told that they may be eligible for enrollment in a clinical trial focused on supporting cancer caregivers. If the caregiver is interested in learning more, the Triage Coordinator will share that caregivers' name and contact information with the study staff to determine interest and eligibility.

Interested participants will be screened and consented over the phone using the verbal consent script, or by EIC (at MGH). Once the caregiver is screened and consented, we will ask if we may contact the patient via phone to introduce the study to him/her.

3) *In-person recruitment*: The research team will screen daily clinic schedules (clinics listed above) to identify patients with upcoming oncology appointments. The treating clinician will either provide the caregiver directly with the contact information of the study team, or give verbal or written email permission to the study team to approach the patient-caregiver dyad at their visit. The timing of this approach will be based on the treating clinician's preference (i.e., before or after the clinic visit). When patients and caregivers are together at the clinic visit, once permission has been granted by the treating clinician to approach, the study CRC will approach both members of the dyad and describe the study. If the caregiver is interested, the CRC will verify eligibility and screen the prospective caregiver with the Distress Thermometer. If eligible, the individual will be consented to the study using the written consent. The CRC will then approach the patient to gauge interest and if interest is expressed, proceed through the screening and enrollment process. These approaches will occur in private areas (i.e. consult rooms) of the above named clinics. If the caregiver and patient prefer to think about possible participation, the CRC will let them know that s/he will follow up with them by phone/email in the next week and will proceed with a verbal consent at that time if applicable.

When a patient is at the clinic without an caregiver, the CRC will provide him/her with information about the study and ask whether the patient has a caregiver who may be interested in taking part in the study. The CRC will provide the patient with contact information for the research team and ask that the patient give this information to the caregiver who can then reach out to the team for more information. If the caregiver consents to participate, we will then ask that caregiver if they would be willing to provide the study team with the contact information of the patient for whom the caregiver provides care to screen and potentially enroll using the verbal consent process or EIC (at MGH).

Caregiver enrollment is not contingent on patient enrollment, and this will be made clear during the consent conversation with patients. It is also not necessary to enroll patients at the same time as caregivers; however, the T1 data collection for patients must occur in advance of caregivers beginning the intervention (either ERT-C or CBT-C).

During the initial conversation between the investigator/research staff and the patient, the patient may be asked to provide certain health information that is necessary to the recruitment and enrollment process. The investigator/research staff may also review portions of their medical records in order to further assess eligibility. They will use the information provided by the patient and/or medical record to confirm that the patient is eligible and to contact the patient regarding study enrollment. If the patient turns out to be ineligible for the research study, the research staff will destroy all information collected on the patient during the initial conversation and medical records review, except for any information that must be maintained for screening log purposes.

In most cases, the initial contact with the prospective participant will be conducted either by the treatment team, investigator or the research staff working in consultation with the treatment team. The recruitment process outlined presents no more than minimal risk to the privacy of the patients who are screened and minimal PHI will be maintained as part of a screening log. For these reasons, we seek a (partial) limited waiver of authorization for the purposes of (1) reviewing medical records to identify potential research subjects and obtain information relevant to the enrollment process; (2) conversing with patients regarding possible enrollment; (3) handling of PHI contained within those records and provided by the potential subjects; and (4) maintaining information in a screening log of patients approached (if applicable).

The screening process for the protocol requires administration of a screening questionnaire (Appendix O and Appendix P). In following the Code of Federal Regulations Title 45, Part 46, Subpart A, which states that an IRB may waive the requirement for an investigator to obtain a signed consent form for some or all subjects if it finds that the research presents no more than minimal risk of harm to subjects and involves no procedures for which written consent is normally required outside of the research context, a signed consent may not be required for this study. In accordance with the aforementioned regulations, we request to waive consent for identifying whether the caregiver is eligible, which includes administering the screening measures, the DT, and one or two subsequent questions as follows: 1) is this distress in any

way related to caregiving, and 2) if no, has this distress started or gotten worse since the patient for whom the caregiver provides care began treatment or was diagnosed. This waiver applies only to MSK patients and their caregivers. If a caregiver is ineligible or does not enroll for any reason following screening, identifying information stored in the screening log will be destroyed.

This limited waiver will apply only to MSK. Any participating sites that require a limited waiver must obtain it from their own local Privacy Board (PB) via a separate protocol addendum or request. It is the responsibility of the MSK staff to confirm the participating data collection site(s) have a limited waiver approved by their local IRB(s)/PBs.

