(T4) 6-month follow-up (after ERT-C/CBT-C last session) = \$20

Caregiver participants will also receive \$10 at the completion of each ERT-C or CBT-C session. Caregivers who complete the entire study (i.e., all 8 sessions and all 4 timepoints) will receive \$130/participant. Patients will be compensated \$25 after the completion of their T3 assessment.

The research team will give the participant a research study receipt (Appendix J) at each timepoint.

Training case participants will not receive compensation.

Biospecimen Collection:

To evaluate inflammatory markers, caregiver participants will provide an oral mucosal transudate (OMT) sample to be collected using the OraSure collection device. MSK staff will mail MSK participants an OraSure collection device, shipping materials, collection diary (Appendix K), a copy of the slides from the instructional video (Appendix N), and a cover letter (Appendix L), MGH staff mail the same materials to participants at MGH and include an intervention-specific welcome sheet at T1 collection (Appendix MGH-H, MGH-I). The research team will email participants with an expected delivery date, a link to an instructional video, and a brief summary of the contents and description of the box. At T1 collection, the package will also include a workbook corresponding to the intervention the participant was randomized to receive (Appendix C, W).

To evaluate diurnal cortisol, caregiver participants will provide saliva samples over three days at each major timepoint. Caregivers will be instructed to swab for 2 minutes and then to remove the pad from the mouth and place it directly in the vial containing an aqueous antimicrobial preservative solution. Caregivers will collect saliva samples upon awakening, 30 minutes later, 8 hours later, and at bedtime.¹⁴⁹ Participants will be instructed to go about their normal daily activities on data collection days and will complete a diary to assess relevant health behaviors (e.g., caffeine, tobacco, and alcohol consumption; physical activity, sleep) and daily stress. To avoid sample contamination, caregivers will be instructed to avoid brushing their teeth, eating, or drinking within 20 minutes pre-sampling (Appendix K, N).

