7.2 Randomization

Participants will be randomized upon registration in CTMS through MSKCC CRDB. Randomization will be 1:1 into ERT-C or CBT-C, stratified by site (i.e., MSK or MGH), using randomly permuted blocks of random length. MSK will provide randomization for both MSK and MGH. MSK will email MGH research staff the randomization results once they are assigned. Training case participants will get assigned to an arm (rather than randomized) based on the needs of our interventionist trainings. MGH participants will be registered in both MSK CTMS and MGH OnCore per MGH policy.

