Power and Sample Size for Aim 1. Preliminary data found ERT-C to have a pre-treatment to post-treatment effect size of $g=0.49$ on depression and anxiety. A recent meta-analysis found very small ($g=0.08$) effects of CBT on these outcomes; this implicates a differential effect size of $d=0.41$. Using an HLM model with up to 3 time points, a within-subject ICC of 0.2, allowing for approximately 20% attrition, and setting Type I error to the conservative value of 0.0125 to account for 4 primary outcomes, we simulate 90.4% power for the differential pre-treatment to post-treatment changes for Aim 1 if the effect size is at least $g=0.41$ and 82.8% power for a more conservative effect of $g=0.37$. Power was simulated using the *simr* [199] package in R. For patient outcomes, the PI anticipates at least 50% enrollment of patients associated to the caregivers, and comparable attrition between patients and caregivers. Enrollment of 120 patients, with 80% retention at the 3-month follow-up assessment will provide 80% power to detect a standardized effect of at least $d=0.63$ for the difference in change scores using an independent samples t-test approximation at alpha of 0.05. Similarly for rumination and worry from pre to post intervention, enrollment of 240 caregivers with 10% attrition during intervention will provide 80% power to detect a medium effect of at least $d=0.50$ with alpha of 0.0125 for these two primary outcomes.

AIM 2: Attention and Metacognitive Regulation Will Have Indirect Effects on the Primary and Secondary Outcomes. Growth curve models will assess overall effects of treatment on primary and secondary outcomes, and the partial mediation of primary outcomes via attention and metacognition regulation skills increases and whether this effect will be more pronounced in ERT-C compared to CBT-C.

Hypothesis 2a: Only skills that specifically target components of distress (i.e., attention regulation, metacognitive regulation) will mediate primary and secondary caregiver outcomes compared to other facets of improving the caregiving experience (i.e., reducing perceived burden, maladaptive behavioral coping).

Hypothesis 2b: These gains and mediation in attention and metacognitive regulation will be more pronounced in caregivers receiving ERT-C as compared to CBT-C.

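### Patients who consent or complete T1 after the caregiver's allocation enter the Hypothesis 1b comparison without the protection of randomization

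*Combined protocol and SAP*

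**What the plan says.** On patient entry, section 7.0 (in-person recruitment) states "It is also not necessary to enroll patients at the same time as caregivers" and sets as the only time limit: "however, the T1 data collection for patients must occur in advance of caregivers beginning the intervention (either ERT-C or CBT-C".

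On allocation, section 7.2 states "Participants will be randomized upon registration in CTMS through MSKCC CRDB". Under section 7.1, registration involves confirming eligibility and obtaining consent. Section 7.2 adds for the second site: "MSK will email MGH research staff the randomization results once they are assigned". Section 4.1 says of the T1 collection kit that "the package will also include a workbook corresponding to the intervention the participant was randomized to receive".

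On the approach to the patient, the remote route reads "Once the caregiver is screened and consented, we will ask if we may contact the patient via phone". Where the patient was seen alone and the caregiver later consents, "we will then ask that caregiver if they would be willing to provide the study team with the contact information of the patient". At a joint clinic visit the patient is approached after the caregiver has consented, and undecided pairs are followed up during the following week.

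On analysis, section 14.0 notes that "the PI anticipates at least 50% enrollment of patients associated to the caregivers". Patient outcomes are analysed as T1-to-T3 change scores regressed on arm with a random site intercept; no covariates are named. The planned comparison by arm covers missing data and attrition. It does not mention patients who never enrolled.

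**The concern.** Randomization balances the arms for people whose membership of the analysis set is settled before allocation, or is unaffected by it. Here a patient can be approached, can agree and can complete baseline after the arm exists and is known to the caregiver and to staff. If the arm influences how hard staff pursue the patient, how the caregiver presents the study, or whether the patient agrees, the two patient groups can differ before any treatment effect.

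A change score removes a difference in baseline level. It does not remove a difference in expected course, for example if declining patients stay out more often in one arm. In patients with any site or stage of cancer, expected course over the follow-up can vary widely. At stake is the interpretation of Hypothesis 1b (patient quality of life, perceived stress and service use).

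**Working it through.** **Step 1: order of events.**

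| Event | When | Source |
|---|---|---|
| Caregiver consent; permission to contact patient sought | Before or at registration | 7.0, 7.1 |
| Caregiver randomized | At registration | 7.2 |
| Arm emailed to second-site staff | Once assigned | 7.2 |
| Arm-specific workbook sent to caregiver | With T1 kit | 4.1 |
| Caregiver T1 saliva sampling | Three days | 4.1 |
| Latest patient T1 | Before session 1 | 7.0 |

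Mailing plus three sampling days leaves an interval of at least some days between allocation and session 1. Patient consent and T1 may fall anywhere in it. No text requires them earlier, and none says that staff recruiting patients are blind to arm.

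**Step 2: the plan's own figure.** 120 patients × 0.80 = 96, or 48 per arm. A two-sample t-test at alpha 0.05 (two-sided assumed; the plan does not say) has 80% power at d = 0.578. At the stated d = 0.63 its power is 86.3%. The stated 0.63 is therefore not reproduced, but it errs on the cautious side and has no bearing on this point. It serves below only as a yardstick.

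**Step 3: possible size.** Every input here is an assumption. Let u be a standardized trait related to joining, with correlation r = 0.3-0.5 with patient change, and no true treatment effect. Then

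spurious difference = r × (mean u of joiners in one arm − mean u of joiners in the other).

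*(a) Same selection rule in both arms, unequal uptake, logistic.* P(join | u) = 1/(1 + exp(−(a + b·u))), with a set to give the stated uptake:

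| Uptake | b | Mean u of joiners | Gap | × 0.3 to 0.5 |
|---|---|---|---|---|
| 55/45 | 0.5 | 0.213, 0.260 | 0.047 | 0.01-0.02 |
| 55/45 | 1.0 | 0.372, 0.455 | 0.083 | 0.02-0.04 |
| 60/40 | 0.5 | 0.189, 0.284 | 0.095 | 0.03-0.05 |
| 60/40 | 1.0 | 0.332, 0.498 | 0.166 | 0.05-0.08 |

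*(b) Upper bound for the same uptake gaps: the trait alone decides who joins.* Mean u = φ(z_p)/p at uptake p.
- 55/45: 0.880 − 0.720 = 0.16; × 0.3 to 0.5 gives 0.05-0.08 SD.
- 60/40: 0.966 − 0.644 = 0.32; × 0.3 to 0.5 gives 0.10-0.16 SD.

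*(c) Selection that itself differs by arm, 50% uptake in both, 48 analysed per arm:*

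| b in the two arms | Gap in mean u | Spurious d | Two-sided error (nominal 5%) |
|---|---|---|---|
| 0.5 and 0 | 0.236 | 0.07-0.12 | 6-9% |
| 1.0 and 0 | 0.413 | 0.12-0.21 | 9-17% |
| 0.5 and −0.5 | 0.472 | 0.14-0.24 | 11-21% |

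If joining does not depend on arm, the bias is 0 and the error rate stays at 5%.

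Against d = 0.63: 0.08/0.63 = 13%, 0.16/0.63 = 25%, 0.24/0.63 = 38%.

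These figures treat every patient as a late entrant. If only a share enters late, with the same uptake early and late, the bias in (c) scales with that share: with half entering late, 0.24 × 0.5 = 0.12. The documents do not give the share.

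**The case against.** The strongest reply is about timing. On the remote and patient-alone routes, the request for access to the patient is tied to the caregiver's consent, and registration follows consent. The caregiver therefore normally decides before an arm exists. At a joint visit the patient may well consent before the caregiver is registered. Section 4.1 also narrates baseline for both members before random assignment. This stands, and it confines the problem to patients who consent or complete T1 late. It does not remove it: permission to make contact is not the patient's consent, and the order of narration is not a rule.

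A second reply is that arm-dependent joining is not very plausible here. Section 4.2 describes both arms as matched in number, frequency and duration of sessions. Patients receive no intervention, and they answer about 14 and 13 minutes of questions at T1 and T3 (sections 9.0 and 11.0). This also stands as a reason to expect a modest effect, but it is not a safeguard.

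A third is that patient outcomes are secondary and lie outside the superiority criterion in section 13.1. That is correct and limits the consequence.

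A reader might infer that Hypothesis 1b is not a randomized comparison at all, or that about half the patients will be chosen by people who know the arm. The documents do not support this. The caregiver's arm is randomized, and patients who enter before allocation keep its full protection. The 50% is a minimum planning figure for uptake, not the share entering late.

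**Conclusion.** The point holds in a limited form. The plan permits patient entry after allocation, with the arm knowable to caregiver and staff, and neither the patient model nor the planned missing-data comparison addresses who joined. For late entrants only, the comparison is not protected by randomization. The documents permit differential entry; they do not show that it will occur.

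The size is unknown. On the assumptions above, unequal uptake alone gives about 0.01-0.08 SD, with 0.05-0.16 SD as the upper bound for those uptake gaps. Only selection that works differently in the two arms reaches about 0.07-0.24 SD. All of these shrink as the share of late entrants falls. A small true patient effect could be obscured or mimicked; a true effect of 0.63 would not be explained away. The caregiver primary analysis is untouched.

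**What to change.** Change the deadline in section 7.0. Before the caregiver's allocation is released, the patient has either consented and completed T1, or is recorded as declined or as not reached by a short fixed cut-off. No patient enters after that. Caregiver enrolment remains independent of patient enrolment, because the cut-off lets allocation proceed either way. Align section 7.2 so that release of the allocation, and mailing of the arm-specific workbook, follow this step.

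For patients already enrolled, use the dates of patient consent, patient T1 and caregiver randomization. Report patient uptake and baseline characteristics by arm and by timing relative to randomization. Add to section 14.0 a sensitivity analysis that repeats Hypothesis 1b in patients who both consented and completed T1 before allocation.

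The cost is an amendment to the order of registration steps, a short wait before allocation, and possibly a few fewer patients. The sensitivity analysis will be less precise than the full comparison, and should be read for agreement in direction and size rather than for significance.
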